12.4.2. Pregnancy

Pregnancies that occur from the time that informed consent is signed through the final follow-up visit will be collected and reported on the Pregnancy Event Form.

If a subject becomes pregnant during the course of the study, she will be instructed to return promptly/within 48 hours of the first notification of pregnancy to the study center and undergo a serum/urine pregnancy test, as confirmation of pregnancy. Every effort will be made to follow-up all pregnancies, including those in the female partner of male subjects, until resolution (ie, termination [voluntary or spontaneous] or birth), providing the volunteers consent to follow-up.

To report a pregnancy, the Pregnancy Event Form must be completed and sent via fax to PPD-PVG within 24 hours of the Investigator or study center staff becoming aware of the pregnancy. The Sponsor provides the Pregnancy Event Form.

Pregnancy itself is not regarded as an AE unless there is a suspicion that the study drug may have interfered with the effectiveness of a contraceptive medication or other AEs were detected.

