^c Visit 6 is the End of Treatment/Early Termination visit. Subjects who discontinue the study prior to Visit 6 will have all Visit 6 procedures performed at the time of discontinuation. All subjects who complete the treatment period and those who discontinue early will complete a follow-up visit 7 (±2) days after the last dose of study drug.

^d Clinical site staff will record the date and time of the 3 doses prior to the study visit in the source (all visits) and CRF (Visits 4 and 6 only), based on subject self-report.

Footnotes continue on next page.

^e Instruct subject to record dosing date and time of the last 3 doses prior to the study visit on the blisterpack wallet and bring back all used/unused study drug and packaging to next visit.

^f Includes a psychiatric history form that will include variables related to duration of illness, treatment response (eg, prior medications used to treat bipolar disorder) and other similar variables.

^g The SCID-5-CT will be used to support the DSM-5 diagnosis and must be administered by a qualified rater at the site.

^h BMI will be calculated by clinical site staff at Screening and recorded in the CRF. At visits 2, 6, and 7, BMI does not need to be calculated by the clinical site staff as it will be calculated in the analysis.

ⁱ Vital signs measurements will include orthostatic changes in blood pressure and heart rate. After being in a supine position for \geq 5 minutes, systolic and diastolic blood pressures, respiratory rate, pulse rate, and temperature will be collected. Blood pressure and pulse rate will be taken again after standing for 2 to 4 minutes. The same arm should be used during each assessment of blood pressure and pulse rate throughout the study.

^j To be eligible for enrollment, subjects must have a MADRS total score \geq 22 at Screening. Subjects who demonstrate a decrease (improvement) of \geq 25% in MADRS total score from Screening to Baseline, or who have a MADRS total score $<$ 22 at Baseline will not be eligible for enrollment (see [Section 24, Appendix V](#)).

^k To be eligible for enrollment, subjects must have a YMRS total score \leq 12 at Screening.

^l At the Screening visit, the baseline/screening version will be completed; for all subsequent visits, the “Since Last Visit” version of the C-SSRS will be administered.

^m Any positive urine β -human chorionic gonadotropin (hCG) test should be confirmed by serum β -hCG.

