10.4. Contraception Requirements

Female Subjects

1. Female subjects of childbearing potential must be using and willing to continue using a highly effective form of birth control for at least 28 days prior to administration of the first dose of study drug, during the treatment period, and 2 months (60 days) after completion or premature discontinuation from the study drug. Highly effective forms of contraception include:
 - Combined estrogen and progestogen containing hormonal contraception (oral, intravaginal or transdermal) associated with inhibition of ovulation.
 - Progestogen-only hormonal contraception (oral, injectable, implantable) associated with inhibition of ovulation.

- Intrauterine device.
- Intrauterine hormone-releasing system.
- Bilateral tubal occlusion.
- Male sterilization (with the appropriate post-vasectomy documentation of the absence of sperm in the ejaculate). For female subjects on the study, the vasectomized male partner should be the sole partner for that subject.
- True abstinence: When this is in line with the preferred and usual lifestyle of the subject. Periodic abstinence (eg, calendar, ovulation, symptothermal, post-ovulation methods) and withdrawal are not acceptable methods of contraception.

Women using hormonal contraception must use an additional form of contraception (eg, condom with spermicide). Because of the unacceptable failure rate of barrier (chemical and/or physical) methods, the barrier method of contraception must only be used in combination with a highly effective method. Post-coital methods of contraception are not permitted. The following is required:

2. A female subject is eligible to enter and participate in the study if she is of:
 - a. Non-childbearing potential (ie, physiologically incapable of becoming pregnant, including any female who is pre-menarchal or post-menopausal);
 - Postmenopausal females defined as being amenorrheic for greater than 2 years (or confirmed by FSH level) with an appropriate clinical profile.
 - Women who have had a hysterectomy, bilateral oophorectomy or bilateral salpingectomy (as determined by subject's medical history).
 - Women who have not been confirmed as postmenopausal and are not surgically sterile should be advised to use contraception as outlined above under number 1.
 - b. Childbearing potential, has a negative pregnancy test at screening and agrees to satisfy one of the following requirements:

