 - Complete abstinence from intercourse (as part of an abstinent lifestyle) a minimum of 2 months (60 days) prior to administration of the first dose of study drug, throughout the Treatment Period, and for a minimum of 3 months (90 days) after completion or premature discontinuation from the study drug; or,
 - Established use of highly effective methods of contraception from 28 days prior to administration of the first dose of study drug, during the Treatment Period, and 2 months (60 days) after completion or premature discontinuation from the study drug. Highly effective methods of birth control are listed above in number 1).

Male Subjects

Male subject with female partner(s) of childbearing potential must ensure that their partner(s) uses the methods of contraception as outlined for female subjects above.

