11.6.4. Follow-up: Visit 7 (Day 49 ± 2)

All subjects will have a follow-up visit 7 days after their last study drug dose. The following study-related procedures will be performed at Visit 7; it is suggested that they be performed in the order presented below, as is possible by the site:

- Administer YMRS.
- Administer PWC.
- Administer C-SSRS (Since Last Visit version).

- Record prior and concomitant medications.
- Record adverse events.
- Perform physical examination.
- Record weight.
- Record waist circumference.
- Obtain vital signs, including orthostatic changes in blood pressure and heart rate.
- Perform 12-lead ECG.
- Collect blood sample(s) for the following clinical laboratory tests:
 - Hematology and Serum Chemistry
 - Serum prolactin
- Collect blood sample for R- and S-amisulpride PK and plasma prolactin analysis.
- Collect urine sample for urine drug screen, urinalysis, and urine β -hCG (female subjects of childbearing potential).

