12.4. Immediately Reportable Events

The following medical events must be immediately reported to the Sponsor:

- **SAE**
- **Pregnancy**

Emergency contact information can be found in Table 1.

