12.4.1. Serious Adverse Event

If the Investigator or study center staff becomes aware of an SAE that occurs in a study subject up to and including the final follow-up, this must be reported immediately to the Sponsor whether considered related or unrelated to the study drug. SAEs must be recorded on the CRF and the data recorded should agree with that on the SAE form.

Following the end of subject participation in the study, the Investigator or an authorized delegate should report SAEs “spontaneously” to the Sponsor PPD Pharmacovigilance (PVG) if considered at least possibly related to the study drug.

SAEs will be followed until resolution, loss to follow-up, stabilization of condition, or the event is otherwise explained.

In addition to the initial telephone notification, an initial SAE form as applicable must be completed and signed and sent via fax or email (see [Table 1](#)) to the Sponsor PPD-PVG within 24 hours of the Investigator or study center staff becoming aware of the event. The SAE form must be signed by the Investigator or appropriate designee. The Sponsor PPD-PVG provides the SAE form used to report SAEs.

SAEs must be promptly reported to the Institutional Review Board (IRB) or Independent Ethics Committee (IEC) by the Principal Investigator or the appropriate person at the study center if required per IRB/IEC guidelines.

The appropriate PVG group must be contacted immediately upon first knowledge of the incident. The immediate report should be made by the Investigator within a very short period of time and under no circumstances should this exceed 24 hours following knowledge of the SAE or pregnancy.

Sunovion will review all SAE reports to determine if any SAEs are suspected unexpected serious adverse reactions (SUSARs).

All fatal or life-threatening SUSARs must be reported as soon as possible, but no later than 7 days after the sponsor first becomes aware of the reaction. Any additional relevant information must be sent within and additional 8 days of the clock date. All non-fatal or non-life-threatening SUSARs must be reported as soon as possible but no later than 15 days after the sponsor first becomes aware of the reaction. Sponsor safety reporting group will notify the applicable Regulatory Agencies of all SUSARs.

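### Protocol 12.4.2 stops collecting pregnancies at the follow-up visit, 5 to 9 days after the last dose, although 10.4 requires contraception for 60 days (90 under one abstinence option)

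*Protocol*

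**What the plan says.** Section 12.4.2 fixes the window by when the pregnancy occurs: "Pregnancies that occur from the time that informed consent is signed through the final follow-up visit will be collected". The final follow-up visit is Visit 7. Footnote c to the Schedule of Assessments (Table 2) says that completers and early discontinuers alike "will complete a follow-up visit 7 (±2) days after the last dose of study drug". Section 11.6.4 repeats the timing ("All subjects will have a follow-up visit 7 days after their last study drug dose") and includes a urine pregnancy test for women of childbearing potential. No later visit or contact is scheduled.

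Section 10.4 sets a longer period for avoiding conception. Item 1 requires highly effective contraception until "2 months (60 days) after completion or premature discontinuation from the study drug", and lists true abstinence among the accepted methods. The first option in item 2b requires complete abstinence "for a minimum of 3 months (90 days) after completion or premature discontinuation from the study drug". Male subjects must ensure that partners of childbearing potential use the same methods; no duration is stated for them.

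On reporting, Section 12.4 lists pregnancy under this instruction: "The following medical events must be immediately reported to the Sponsor". Section 12.4.1 adds that "under no circumstances should this exceed 24 hours following knowledge of the SAE or pregnancy", and 12.4.2 asks for the Pregnancy Event Form "within 24 hours of the Investigator or study center staff becoming aware of the pregnancy". None of these three statements has an end date. Section 12.4.2 also commits the study to following pregnancies, including those of male subjects' partners, to their outcome, subject to consent.

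**The concern.** By requiring contraception for 60 days after dosing, the sponsor has marked out a period in which conception is to be avoided. Routine collection ends 5 to 9 days into that period. Nothing in the Visit 7 procedures asks a subject to tell the site about a later pregnancy, and a site reading 12.4.2 literally could conclude that a conception 30 days after the last dose is out of scope.

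The drafters did write a rule for events after participation ends (12.4.1), but it covers only SAEs judged at least possibly related to study drug. Section 12.4.2 says that a pregnancy is not in itself normally an adverse event, so an uneventful late pregnancy does not fall under that rule.

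What is at stake is the completeness of pregnancy safety information for an investigational drug. No efficacy endpoint, error rate or power figure depends on it.

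**Working it through.** The plan states no figure for this gap, so there is nothing to reproduce. The check is a day count.

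Inputs:
- Visit 7: 7 ± 2 days after the last dose (Table 2, footnote c), so day 5 at the earliest and day 9 at the latest.
- Contraception after the last dose: 60 days (10.4 item 1, and the contraception option in item 2b).
- Abstinence after the last dose: 90 days (10.4 item 2b, abstinence option only).

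Formula: days outside the collection rule = required days after the last dose − day of Visit 7.

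| Requirement | Visit 7 on day 9 | Visit 7 on day 5 | Share of post-dose period |
|---|---|---|---|
| 60 days | 60 − 9 = 51 | 60 − 5 = 55 | 51/60 = 85% to 55/60 = 92% |
| 90 days (item 2b abstinence) | 90 − 9 = 81 | 90 − 5 = 85 | 81/90 = 90% to 85/90 = 94% |

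The rule turns on when a pregnancy occurs, not when it is detected. Every conception from consent to Visit 7, including all of those during dosing, is therefore inside it, even if recognised weeks later. Only conceptions after Visit 7 are outside.

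I then looked for text that moves the end date:
- The 24-hour rule starts when the site becomes aware. It covers a late pregnancy that is volunteered but does not prompt anyone to volunteer it.
- The commitment to follow pregnancies to resolution concerns the outcome of known pregnancies. It does not find new ones.
- Section 12.4.2 tells a subject who becomes pregnant while the study is running to return for a confirmatory test. Table 4 defines the end of the study by the last subject's last visit, so on one reading this instruction outlasts a subject's own Visit 7. It still does not change the collection window, and the last subject gains no extra days.
- The post-participation SAE rule would bring in a congenital anomaly considered possibly related (12.1.2 and 12.4.1), but not the pregnancy itself.

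None of these extends collection past Visit 7.

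**The case against.** The strongest reply is that pregnancies conceived during dosing are already inside the rule and the rest are largely covered. Conceptions up to Visit 7 count whenever they are recognised, and urine tests are done at Visits 2, 4, 6 and 7. A later pregnancy is immediately reportable once the site knows of it, and known pregnancies are followed to outcome. A contraception period and a collection period need not be equal, and without a half-life the documents cannot show that a conception after Visit 7 is drug-exposed. The consent form is not in the copy reviewed and may already ask subjects to report later pregnancies. The proposed change would still rely on self-report.

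Most of this stands, and it is why the point is minor. It does not remove the mismatch: 12.4.2 states an end date well short of the period in 10.4, and a late pregnancy reaches the sponsor only if someone happens to mention it.

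A reader might also infer three stronger things that the documents do not support:
- *That follow-up of known pregnancies is deficient.* Section 12.4.2 carries known pregnancies to resolution. The affected step is collection.
- *That 90 days is the general standard.* It appears only in the item 2b abstinence option and conflicts with item 1, which places true abstinence under 60 days. It may not apply in Poland, where inclusion criterion 9, as given in SAP Appendix 7, has no abstinence option.
- *That 85% to 94% of late pregnancies would be missed.* Those are shares of calendar days, not of pregnancies.

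**Conclusion.** The concern holds as a minor design point. Conceptions in 51 to 55 of the 60 post-dose days (81 to 85 of 90 under the item 2b abstinence option) fall outside the stated collection rule, and their capture depends on the site learning of them. Collection in that period may be incomplete; the text does not show that it will be.

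This rests on reading the window in 12.4.2 by date of conception and on taking Visit 7 within its ±2-day window. The number of pregnancies affected cannot be estimated, because the documents give no rate. I assume few, given that effective contraception is required throughout. I give no share of the whole contraception period including the pre-dose days: collection starts at consent, so some pre-dose days also lie outside it and such a share would mislead.

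**What to change.** In Section 12.4.2, replace the end point at the final follow-up visit with the end of the contraception period required by Section 10.4: 60 days after the last dose, and 90 days for subjects under the item 2b abstinence option unless 10.4 is harmonised to 60. Harmonising is the cleaner course, since items 1 and 2b now disagree on abstinence. State the same 60-day period for partners of male subjects, for whom 10.4 gives no duration. In Section 11.6.4, add a Visit 7 reminder to tell the site of any pregnancy in that period, reported on the existing Pregnancy Event Form under the existing 24-hour rule.

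The cost is a wording amendment with IRB/IEC approval (17.5) and re-consent of affected enrolled subjects (17.3) across approximately 85 sites. The Japan and Poland amendments named in the SAP introduction may need matching changes. A few late reports, possibly with a confirmatory test, would be held in the safety database. No scheduled visit or routine test is added, so capture still depends on self-report. The change could be combined with another amendment.

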12.5. Data and Safety Monitoring Board

A Data and Safety Monitoring Board (DSMB) will review safety data at regular intervals. The DSMB will be independent of the Sponsor, CRO, and the Investigators and will be empowered to recommend stopping the study due to safety concerns, but not for efficacy or futility. The DSMB may review blinded, unblinded, or partially unblinded data, but the Sponsor (with the exception of the relevant members of the pharmacovigilance team responsible for reporting Suspected Unexpected Serious Adverse Reactions [SUSARs]), the CRO, and the Investigators will remain blinded until the official unblinding of the database. The membership of the DSMB and its mandate will be described in a separate DSMB charter.

13. TERMINATION OF SUBJECT FROM STUDY/ DISCONTINUATION OF STUDY DRUG

13.1. Criteria for Subject Termination

Subjects may terminate the study participation at any time for any reason.

The possible reasons for the termination of study participation are as follows:

- Adverse event.
- Lack of efficacy (specify).
- Lost to follow-up (specify).
- Pregnancy.
- Withdrawal by subject (specify).
- Non-compliance with study drug (specify).
- Protocol deviation (specify).
- Death
- Other (specify).

If at any time during the course of the study, in the opinion of the Investigator, the subject may no longer safely participate due to a change in medical status (eg, experiences an AE, becomes pregnant), the subject must be discontinued from the study drug.

Subjects who, at any study visit post-baseline have a QTcF value greater than 500 ms, who have a > 60 ms increase in QTcF from baseline, or who experience a life-threatening arrhythmia will be discontinued from the study drug and followed until the event resolves; in addition, an adverse event will be reported.

Subjects who develop adverse events of amenorrhea, gynecomastia, or galactorrhea are to be discontinued from the study drug. The reason for discontinuation and information on the epoch will be recorded on the appropriate CRF. In case of death, the date of death should be captured on the CRF.

Subjects who prematurely terminate the study participation will not be replaced.

Subjects who discontinue prior to Visit 6 (Day 42 [± 2]) will undergo procedures and assessments scheduled for Visit 6 (Day 42 [± 2]) at the time of early discontinuation (see [Section 11.6.3](#)).

14. STUDY TERMINATION

The Sponsor reserves the right to discontinue the study at this study center or at multiple centers for safety or administrative reasons at any time while safeguarding that early termination does not compromise subjects' safety or well-being. In particular, a study center that does not recruit at an acceptable rate may be closed. Should the study be terminated and/or the study center closed for whatever reason, all documentation and study medications pertaining to the study must be returned to the Sponsor or its representative.

If, in the opinion of the Investigator, clinical observations suggest it may be unsafe to continue, the Investigator may terminate part or the entire study after consultation with the Sponsor.

In the event of study or site termination, subjects will be required to return for a final study assessment 7 days after their last dose of study drug (ie, follow-up) and be provided with access to standard care.

15. STATISTICS

The comprehensive statistical analysis plan (SAP) will provide details on the statistical methods planned for this study and will be finalized prior to the US and Europe cohort unblinding.

15.1. Sample Size

A total sample size of 279 evaluable subjects in US and Europe (93 per treatment group: SEP-4199 200 mg/day, SEP-4199 400 mg/day, and placebo) with a global 2-sided alpha of 0.05 will provide about 90% power to reject at least 1 truly significant comparison and about 75% power to reject both truly significant comparisons using the truncated Hochberg ($\gamma = 0.9$) procedure, assuming treatment effect sizes of 0.44 for both doses of SEP-4199. The effect sizes were selected considering the data from the completed lurasidone bipolar depression study ([Loebel 2014](#)). This effect size corresponds to a treatment difference of -3.85 for a SEP-4199 dose with a common standard deviation of 8.745 on the MADRS scale change from baseline at Week 6. An upward adjustment of approximately 5% is used to compensate for information lost due to subjects who are randomized and do not provide any postbaseline primary efficacy data. The total sample size will be approximately 294 randomized subjects (or $N = 98$ subjects per treatment group).

For the secondary efficacy endpoint, assuming the 93 subjects per treatment arm, the study will have 71% power to reject at least one truly significant comparison within the CGI-BP-S family using the regular Hochberg procedure, given a treatment difference of -0.47 for a SEP-4199 dose with a common standard deviation of 1.24 on the CGI-BP-S change from baseline at Week 6. The correlation between the primary and the secondary endpoint is assumed to be 0.8 for each treatment arm.

The sample size was calculated using the Mediana package version 1.05 within R version 3.4.2 ([R Core Team 2017](#)).

The sample size for the Japanese cohort (45 total [$N = 15$ subjects per group], including 9 dropouts) provides more than 80% probability to have a treatment difference point estimate greater than zero for the MADRS.

